#### 7.4. Laboratory Procedures

Not applicable.

### 8. SUBJECTS COMPLETION/WITHDRAWAL

#### 8.1. Completion Criteria

Subjects are considered to have completed the study if they:

- Provided informed consent;
- They are eligible;
- Completed all study visits;
- Have not withdrawn/discontinued from the study for any reason described in Section 8.2

#### 8.2. Withdrawal/Discontinuation from the Study

A subject will be withdrawn from the study for any of the following reasons:

- Subject death during the study period
- Subject withdrawal of consent
- Subject not compliant to the study protocol including drop usage schedule
- Subject lost to follow-up
- Subject no longer meets eligibility criteria (e.g. the subject becomes pregnant)
- Subject develops significant or serious adverse events causing discontinuation of study drop
- Subjects who have experienced a Corneal Infiltrative Event (CIE)
- Investigator's clinical judgment regarding the subject safety reasons (that it is in the best interest of the subject to stop treatment)

- Subject not successfully dispensed due to lack of efficacy or safety

For discontinued subjects, the Investigator will:

- Complete the current visit (scheduled or unscheduled)
- Complete the Final Evaluation, indicating the reason that the subject was discontinued from the study
- Collect used test article(s) (brought to the visit) from the subject and discard them, unless otherwise stated in Section 7.2
- Collect all unused test article(s) from the subject

An additional subject may be enrolled if a subject discontinues from the study prematurely.

In cases where a subject is lost to follow-up, every possible effort must be made to contact the subject and determine the reason for discontinuation/withdrawal. The measures taken to follow up must be documented including two written attempts and a certified letter (or equivalent) as the final attempt.

## **9. PRE-STUDY AND CONCOMITANT INTERVENTION/MEDICATION**

Concomitant medications will be documented during screening and updated during the study. Disallowed medications for this study include: Current habitual use of Prescription Only Medicines for dry eye or ocular discomfort, ocular steroids, or any medication (RX or OTC) that would interfere with the clinical study (at the discretion of the investigator).

Concomitant therapies that are disallowed include: Current habitual use of Prescription Only Medicines for dry eye or ocular discomfort, ocular steroids, or any medication (RX or OTC) that would interfere with the clinical study (at the discretion of the investigator).

## **10. DEVIATIONS FROM THE PROTOCOL**

Investigator will notify study sponsor upon identification of a protocol deviation. Major protocol deviations must be reported to the sponsor within 24 hours after discovery of the protocol deviation. The Investigator will report deviations per IRB/IEC requirements. All deviations will be tracked and corrective actions implemented as appropriate.

If it becomes necessary for the Investigator to implement a deviation to eliminate an immediate hazard to the trial subject, the Investigator may implement the deviation immediately without notification to the sponsor. Within 24 hours after the implemented deviation, the Investigator must notify and provide the rationale to the Sponsor and, as required, the IEC/IRB.

The prescribed visit window for Visit 2 is 7 +/- 1 days from Visit 1 (Day 0), and for Visit 3 is 30 +/- 2 days from Visit 1. Subjects that complete Visit 2 five (5) days or nine (9) days from Visit 1, or complete Visit 3 twenty-seven (27) or thirty-three (33) days from Visit 1, will be categorized as a minor protocol deviation. Subjects completing Visit 2 at 4 days or earlier or 9 days or later from Visit 1 will be categorized as a major protocol deviation. Subject completing Visit 3 at 27 days or earlier, or 34 days or later from Visit 1 and these subjects or completing Visit 3 at 27 days or earlier will also be categorized as a major

protocol deviation. These subjects with major PDs will be excluded from the primary study analysis.

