### **2.2. Endpoints**

#### **Primary Endpoint:**

The primary endpoint in this study is change in overall ocular comfort score from baseline at 30-Day follow-up. Subjective overall ocular comfort will be assessed at baseline, 7-Day and 30-Day follow-up using a Visual Analogue Scale (VAS) with continuous scale from 0 (extremely uncomfortable) to 100 (extremely comfortable).

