### **2.3. Hypotheses**

#### **Primary hypotheses:**

1. The Test eye drops will be non-inferior to the Control eye drops with respect to change in ocular comfort from baseline at 30-Day follow-up. A non-inferiority margin of -20 point ocular comfort VAS scale will be used.

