## 4. STUDY DESIGN AND RATIONALE

### 4.1. Description of Study Design

This is a 30-Day multi-site, randomized, double masked, bilateral, controlled, 2-Arm parallel group study. Approximately 150 subjects will be screened and randomly assigned to either Test or Control group (60 subjects/arm). The goal is for a sample size of 112 after subjects who withdraw or are lost-to-follow-up. Subjects are scheduled for 3 study visits (screening/baseline, 7-Day and 30-Day follow-up visits) over a period of one month.

At Visit 1, subjects will be consented and screened for inclusion/exclusion criteria. If a subject is found to meet all eligibility criteria, they will be dispensed with artificial tears eye drops based on the randomization scheme; otherwise, the subject will be discontinued from the study. Subjects will be dispensed with their randomly assigned eye drops and instructed to use them in both eyes, 3-4 times a day over a  $7\pm1$  day period. The follow-up evaluation (Visit 2) will occur  $7\pm1$  days after Visit 1.

At Visit 2, VAS and PRO questionnaires, SROS and slit lamp findings will be evaluated, and the subject will be dispensed with a new bottle of drops. Subjects will be instructed to use them in both eyes 3-4 times a day until the next scheduled study visit. Visit 3 will take place  $30\pm2$  days after Visit 1.

At Visit 3, VAS and PRO questionnaires, SROS, NITBUT and slit lamp findings will be evaluated, and the subject will have a final evaluation before exiting from the study.

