### **14.2. Sample Size Justification**

The sample size was calculated to test for non-inferiority of the Test relative to Control eye drops with respect to the ocular comfort score using VAS with a minimum power of 85% and a two-sided type I error of 0.05. Assuming a difference between the Test and Control of 20, a common standard deviation (SD) of 35, the estimated sample size for non-

inferiority was 56 per treatment group using two-sample t-test. The sample size calculation was performed using the SAS procedure PROC POWER. The common standard deviation considered was based on results from [REDACTED] in which the estimated standard deviation of change in ocular end of day comfort from baseline at 30-day in the control group was estimated to be 2.53 in a VAS scale from 0 to 10 [REDACTED]

[REDACTED] We increased the standard deviation by one unit in case more variation will be observed in the Test group. Therefore, the standard deviation used in the sample calculation was 35 in a VAS scale from 0 to 100 ( $35 = 10 * (2.5 + 1)$ ).

The plan is to enroll 150 eligible subjects (60 per arm) with a target completion of 112 (56 per arm). During the enrollment period, the subject dropout rate will be closely monitored, if unexpectedly high dropout rate is observed (>10%) in certain arm(s), the targeted total enrollment number might be increased accordingly in order to ensure a minimum of 56 subjects per group to complete the 1-month follow-up.

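### Section 10 lets Visit 2 timing decide who enters the Day-30 primary analysis, classes two visit days as both minor and major, and does not match the Per-Protocol definition in Section 14.3

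*Combined protocol and SAP*

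**What the plan says.** Section 2.2 fixes the time point: "The primary endpoint in this study is change in overall ocular comfort score from baseline at 30-Day follow-up". Sections 14.3 and 14.5 make Per-Protocol the primary population, with ITT as a sensitivity analysis.

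Section 10 sets windows of 7 ± 1 days for Visit 2 and 30 ± 2 days for Visit 3, both counted from Visit 1. Its minor class contains Days 5 and 9 for Visit 2 and Days 27 and 33 for Visit 3. Its major class for Visit 2 is worded "Subjects completing Visit 2 at 4 days or earlier or 9 days or later from Visit 1". For Visit 3 the major class is Day 27 or earlier, or Day 34 or later, in a sentence whose wording is damaged. The paragraph ends: "These subjects with major PDs will be excluded from the primary study analysis". It makes no exception for a subject whose only major deviation is at Visit 2.

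Section 14.3 defines Per-Protocol differently. Subjects must have completed all visits and must not have deviated substantially, as decided by a cohort review committee before database lock, with the reasons documented.

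The sample size in Section 14.2 is for a non-inferiority test "with a minimum power of 85% and a two-sided type I error of 0.05".

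**The concern.** A subject seen on Day 10 and again on Day 30 has a baseline score and an on-time Day-30 score, which are the two values the primary endpoint needs. Visit 3 is scheduled from Visit 1, so a late Visit 2 does not move the Day-30 measurement. Section 10 still removes the whole subject.

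Three things are at stake:

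- **Definition of the primary set.** Two visit days fall in both classes, and two sections give different routes to exclusion. Two analysts could build different primary sets from the same data.
- **Precision.** The step from 60 to 56 per arm in Section 4.3 allows for withdrawal and loss to follow-up only. The enrolment increase in Section 14.2 is triggered by dropout, and replacement in Sections 4.3 and 8.2 by discontinuation. A subject who attends Visit 2 late and finishes the study is neither.
- **Selection.** Visit 2 attendance comes after randomization. If it depended on comfort with the assigned drop, the exclusions could differ between arms.

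**Working it through.** **1. Day limits side by side (Section 10)**

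| Visit | In window | Minor | Major | In both classes |
|---|---|---|---|---|
| 2 | Days 6–8 | Days 5, 9 | Day 4 or earlier; Day 9 or later | Day 9 |
| 3 | Days 28–32 | Days 27, 33 | Day 27 or earlier; Day 34 or later | Day 27 |

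For Visit 2, only Day 4 or earlier and Day 10 or later are unambiguously major. Day 5 is minor and stays in. The fate of Day 9, and of Day 27 at Visit 3, cannot be read from the text.

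**2. Does the primary model need the Day-7 value?** Section 14.5 plans a mixed model for repeated measures over Days 0, 7 and 30 with an unstructured covariance. Such a model accepts a subject with Days 0 and 30 only, so setting aside an out-of-window Day-7 score does not require deleting the subject.

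**3. Reproducing the planned sample size.** Inputs from Section 14.2: "Assuming a difference between the Test and Control of 20, a common standard deviation (SD) of 35". The margin is in Section 2.3: "A non-inferiority margin of -20 point ocular comfort VAS scale will be used". The 20 is read as the distance from a true difference of 0 to the margin. Two-sided 0.05 is one-sided 0.025.

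With n per arm, the non-centrality is 20 / (SD × √(2/n)) on 2n − 2 degrees of freedom. Power is the probability that this non-central t exceeds the 97.5% point of the central t.

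At n = 56 and SD 35: 20 / (35 × √(2/56)) = 3.024, critical value 1.982, power 85.02%. At n = 55 power is 84.4%, below the target. This reproduces the stated result ("inferiority was 56 per treatment group using two-sample t-test") and shows that 56 has no slack at SD 35.

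**4. Power after Visit 2 exclusions.** The documents give no rate of major Visit 2 deviations, so the rates below are assumptions applied to 56 per arm. The SD of 25.3 is the observed 2.53 on the 0–10 scale times 10. Section 14.2 adds one unit to that SD to reach 35.

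| Assumed share excluded | n per arm | Power, SD 35 | Power, SD 25.3 |
|---|---|---|---|
| 0% | 56 | 85.0% | 98.6% |
| 2% | 55 | 84.4% | 98.4% |
| 5% | 53 | 83.0% | 98.1% |
| 10% | 50 | 80.8% | 97.5% |
| 15% | 48 | 79.1% | 97.0% |

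Starting from 60 randomized per arm, 56 remain only if dropout and Per-Protocol exclusions together are at most 4/60 = 6.7%.

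**5. Selection, as illustration only.** Suppose a share q of the Test arm is excluded, their Day-30 change is D points worse than that of the retained Test subjects, and Control has no such selection. The Per-Protocol estimate then favours Test by q × D. At a true full-population difference of −20 with SD 35:

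- q = 5%, D = 10: bias 0.5 points; one-sided error about 3.0% instead of 2.5%.
- q = 10%, D = 20: bias 2.0 points; one-sided error about 4.8%.

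Neither q nor D comes from the documents.

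**The case against.** The strongest reply is that a late Visit 2 can matter to a per-protocol question. Visit 2 is a dispensing visit: step 1.24 supplies drops for about a week, and steps 2.3 and 2.14 collect the bottle and issue a new supply. A visit well past Day 8 could leave a gap in treatment. This stands as a reason to consider exclusion. It does not make the visit date the right criterion, because drop use is checked directly at steps 2.2 and 3.2.

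Other points that stand:

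- Per-Protocol is a customary population for non-inferiority, and the committee in Section 14.3 might keep some of these subjects.
- The damaged Visit 3 sentence allows the closing exclusion to be read as covering Visit 3 deviators only. The broader reading is more natural, since the closing words refer to major deviations without naming a visit.
- Section 20 lets the sponsor withhold payment for visits scheduled out of range, which should keep such deviations uncommon.
- Section 14.1 defers detail to a stand-alone SAP.

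A reader might infer several stronger things that the documents do not support:

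- **That a Day 9 visit is certainly excluded.** Section 10 also calls it minor.
- **That on-time Day-30 scores are thrown away.** They leave the primary set but remain in the ITT analysis.
- **That the trial becomes underpowered.** Falling below 85% needs both the deliberately raised SD and an assumed exclusion rate.
- **That the primary result is biased.** Nothing links Visit 2 timing to comfort or to arm, and subjects and investigators are masked.

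**Conclusion.** The point holds as a defect in how the primary analysis set is defined. On the plain reading, a clearly major Visit 2 deviation removes an on-time Day-30 score from the primary analysis. Visit 2 on Day 9 and Visit 3 on Day 27 have no defined status. Automatic exclusion in Section 10 and committee judgment in Section 14.3 cannot both govern.

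The power consequence is modest. At SD 35 and a true difference of 0, it is about 2 percentage points at 5% excluded and about 4 at 10%. With an SD near 25.3 it is about 1 point or less up to 10% excluded, and power stays far above 85%. That 25.3 comes from end-of-day comfort in the control group of a previous study, so it is a guide and not a certainty for overall comfort here. Selection is a possibility that more enrolment would not remove, but its size cannot be taken from the documents.

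**What to change.** Before database lock, amend Sections 10 and 14.3 and carry the same wording into the stand-alone SAP:

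1. Reconcile the minor and major day limits for both visits so that each day falls in one class, and repair the Visit 3 sentence.
2. State whether timing exclusions are automatic or decided by the committee, and use the same rule in both sections. Say explicitly whether a missed Visit 2 alone removes a subject from the Day-30 analysis, since Section 14.3 now requires all visits.
3. Make the timing exclusion visit-specific. An out-of-window Visit 2 should affect only the Day-7 value and the Day-7 secondary analyses. Visit 3 timing should govern the Day-30 primary analysis.
4. Base any Per-Protocol exclusion for a gap in drop use after a late Visit 2 on the compliance recorded at steps 2.2 and 3.2, not on the Visit 2 date.

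This needs no new data collection and no change of model. The cost is wording and a slightly less strict Per-Protocol definition.

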## **11. STUDY TERMINATION**

The occurrence of one or more Unanticipated Serious Adverse Device Effect (USADE), or any SAE where the relationship to study agent cannot be ruled out, may result in stopping further dispensing of test article. In the event of a USADE or SAE, the Sponsor may unmask the treatment regimen for the subject(s) and will discuss this with the Investigator before any further subjects are enrolled.

The Sponsor will determine when a study will be stopped. The Principal Investigator always has the discretion to initiate stopping the study based on patient safety or if information indicates the study's results are compromised.

JJV reserves the right to terminate the study at any time for any reason. Additionally, the IEC/IRB reserves the right to terminate the study if an unreasonable risk is determined. The study can be terminated by the Principal Investigator at the individual clinical site due to specific clinical observations, if in their opinion, after a discussion with JJV, it is determined that it would be unwise to continue at the clinical site.

JJV (and the IEC/IRB and DMC, if applicable) will evaluate all adverse events. If it is determined that an adverse event presents an unreasonable risk, the investigation, or that part of the investigation presenting the risk, will be terminated, as soon as possible.

Should the study be terminated (either prematurely or as scheduled), the Investigator will notify the IEC/IRB and Regulatory Authority as required by local regulatory requirements.

## **12. PROCEDURE FOR HANDLING PRODUCT QUALITY COMPLAINTS**

A Product Quality Complaint (PQC) refers to any written, electronic, or oral communication that alleges deficiencies related to the identity, quality, durability, reliability, safety, effectiveness or performance of test articles after they have been released for clinical trial use.

Potential complaints may come from a variety of sources including but not limited to subjects, clinical research associates (CRA), clinical operations managers (COM), medical monitors, and site personnel, etc. The following are not considered PQCs:

- Subject satisfaction inquiries reported via "Subjective Questionnaires" and "Patient Reported Outcomes (PRO)"
- Clinical test articles that are stored improperly or damaged after receipt at the investigational site
- Artificial tear replacements that occur due to loss/run out
- Damage deemed by clinicians or clinical staff to be caused by handling by the user, and not indicative of a quality deficiency, only in situations where there is no deficiency alleged by the subject

Within 24 hours of site personnel becoming aware that a PQC has occurred, the PQC must be recorded in the EDC system, which will trigger an automatic email notification to the

appropriate COM/CRA and Clinical QA representative. In cases where the EDC system in use is not configured to send automatic notifications or when an EDC system is not used, the COM/CRA is responsible for notifying Clinical QA upon discovery that a PQC has occurred.

Upon receipt of the EDC notification, the COM/CRA will contact the study site to collect additional information which will include:

- Date the complaint was received/recorded in the EDC System (Date of Sponsor Awareness)
- Who received the complaint
- Study number
- Clinical site information (contact name, site ID, telephone number)
- Lot number(s)
- Unique Subject Identifier(s)
- Indication of who first observed complaint (site personnel or subject)
- OD/OS indication, along with whether the drops were inserted
- Any related AE number, if applicable
- Detailed complaint description (scheduled/unscheduled visit, symptoms, resolution of symptoms, etc.)
- Eye Care Provider objective (slit lamp) findings if applicable
- Confirmation of product availability for return (and tracking information, if available), or rationale if product is not available for return

[REDACTED]

[REDACTED]

Once a complaint is received, it will be assessed by the COM, CRA, or trained site personnel to determine if it is an Adverse Event/Serious Adverse Event (AE/SAE). If the complaint results in an AE/SAE, the COM/CRA, or trained site personnel will follow Section 13 of this protocol. If the AE/SAE was potentially the result of a product quality related deficiency, these procedures also applies and will be executed in parallel.

In some cases, a PQC form may be generated in EDC by the site in error. In this event, the PQC forms will be marked “Intentionally Left Blank” or “ILB”. Justification for ILB must be documented.

## 13. ADVERSE EVENTS

### 13.1. Definitions and Classifications

**Adverse Event (AE)** – An AE is “any untoward medical occurrence, unintended disease or injury, or untoward clinical signs (including abnormal laboratory findings) in subjects, users or other persons, whether or not related to the investigational medical device.

*Note 1* to entry: This definition includes events related to the investigational medical device or the comparator.

*Note 2* to entry: This definition includes events related to the procedures involved.

*Note 3* to entry: For users or other persons, this definition is restricted to events related to investigational medical devices.”

An AE includes any condition (including a pre-existing condition) that:

1. Was not present prior to the study, but appeared or reappeared following initiation of the study
2. Was present prior to the study but worsened during the study. This would include any condition resulting from concomitant illnesses, reactions to concomitant medications, or progression of disease states
3. Pregnancy must be documented as an adverse event and must be reported to the clinical monitor and to the Sponsor immediately upon learning of the event

**Serious Adverse Event (SAE)** – An SAE is any untoward medical occurrence that:

- Results in death
- Is life threatening
- Requires in-patient hospitalization or prolongation of existing hospitalization
- Results in persistent or significant disability/incapacity (e.g., a sight threatening event, a significant persistent or permanent change, impairment, damage, or disruption to the subject's body)
- Is a congenital anomaly/birth defect, or
- Requires intervention to prevent permanent damage (the use of the test article resulting in a condition which requires medical or surgical intervention to preclude permanent impairment of the body structure or a body function). Important medical events that may not result in death, be life-threatening, or require hospitalization may be considered an SAE when, based upon appropriate medical judgment, they may jeopardize the patient or subject and may require medical or surgical intervention to prevent one of the outcomes listed in the above definition

Diagnoses and conditions that are considered Ocular Serious Adverse Events include, but not limited to:

- Microbial Keratitis (MK)
- Iritis (including cells in the anterior chamber)
- Permanent decrease in best spectacle corrected visual acuity equivalent to 2 acuity lines or greater
- Central Corneal Opacity
- Central Corneal Neovascularization
- Uveitis
- Endophthalmitis
- Hypopyon
- HypHEMA
- Penetration of Bowman's Membrane
- Persistent Epithelial Defect
- Limbal cell Damage leading to Conjunctivalization

**Significant Adverse Events** – Those events that are usually symptomatic and warrant discontinuation (temporary or permanent) of the test article (excluding Serious Adverse Events).

Diagnoses and conditions that are considered Ocular Significant Adverse Events include, but not limited to the following:

- Significant Infiltrative Events (SIE)
- Keratoconjunctivitis (toxic or infectious)
- Chemical Keratitis

- Any Temporary Loss of >2 Lines of BSCVA
- Other Grade 3 or higher corneal findings, such as abrasions or edema
- Corneal events - e.g. Epidemic Keratoconjunctivitis (EKC)
- Asymptomatic Corneal Scar
- Any corneal event which necessitates temporary lens discontinuation >2 weeks

**Non-Significant Adverse Events** – Those conditions that are usually asymptomatic and usually do not warrant discontinuation (temporary or permanent) of the test article. However, the Investigator may choose to treat as a precautionary measure.

Diagnoses and conditions that are considered Ocular Non-Significant Adverse Events include, but not limited to the following:

- Non-significant Infiltrative Event (NSIE)
- Papillary Conjunctivitis
- Corneal abrasions
- Superficial Punctate Keratitis (SPK)
- Conjunctivitis: Bacterial, Viral, Allergic
- Blepharitis
- Meibomianitis
- Contact Dermatitis
- Localized Allergic Reactions or infections
- Temporary visual disturbances (blurriness)
- Any corneal event not explicitly defined as serious or significant adverse event, which necessitates temporary discontinuation of the drops <2 weeks

**Adverse Device Effect (ADE)** – An ADE is an “adverse event related to the use of an investigational medical device.

*Note 1* to entry: This definition includes adverse events resulting from insufficient or inadequate instructions for use, deployment, implantation, installation, or operation, or any malfunction of the investigational medical device.

*Note 2* to entry: This definition includes any event resulting from use error or from intentional misuse of the investigational medical device.”

**Unanticipated Adverse Device Effect (UADE)** – Any serious adverse effect on health or safety or any life-threatening problem or death caused by, or associated with, the test article, if that effect, problem, or death was not previously identified in nature, severity, or degree of incidence in the investigational plan, Investigator’s Brochure or protocol, or any other unanticipated serious problem associated with the test article that relates to the rights, safety and welfare of subjects.

